5.5.10 Withdrawal of consent

Patients may voluntarily withdraw consent to participate in the study for any reason at any time.

Withdrawal of consent occurs only when a patient does not want to participate in the study anymore, and does not want any further visits or assessments, and does not want any further study-related contacts, and does not allow analysis of already obtained biologic material.

If premature withdrawal occurs for any reason, the investigator must make every effort (e.g. telephone, e-mail, letter) to determine the primary reason for this decision and record this information on the appropriate study completion eCRF.

Patients who prematurely discontinue or withdraw during a specific treatment period should return for a final visit (see [Table 6-1](#)). The final visit should be scheduled approximately four weeks after the last study treatment, and should be performed before any new treatment is initiated.

Patients who are prematurely withdrawn from the study will not be replaced by newly enrolled patients.

5.5.11 Loss to follow-up

For patients who are lost to follow-up (i.e., those patients whose status is unclear because they fail to appear for study visits without stating an intention to withdraw), the investigator should show "due diligence" by documenting in the source documents steps taken to contact the subject, e.g. dates of telephone calls, registered letters, etc.

5.5.12 Emergency breaking of assigned treatment code

Emergency treatment code breaks should only be undertaken when it is essential to treat the subject safely and efficaciously. Most often, study discontinuation and knowledge of the possible treatment assignments are sufficient to treat a study subject who presents with an emergency condition.

Emergency treatment code breaks are performed using the IRT. When the investigator contacts the system to break a treatment code for a subject, he/she must provide the requested subject identifying information and confirm the necessity to break the treatment code for the subject. The investigator will then receive details of the investigational drug treatment for the specified subject and a fax or email confirming this information. The system will automatically inform the Novartis and CRO study personnel that the code has been broken.

It is the investigator's responsibility to ensure that there is a procedure in place to allow access to the IRT in case of emergency. The investigator will inform the subject how to contact his/her backup in cases of emergency when he/she is unavailable.

5.5.13 Study completion and post-study treatment

A subject's individual study participation is completed once Visit 19/Week 52 Treatment Period has been completed. Any SAEs that occur in the following 84 days (12 weeks) after the dose of study drug must be reported. The investigator will also follow any AEs for which there is no outcome that can be reported at the final study visit.

The study as a whole will be completed once all randomized patients have completed the study as per the protocol and the clinical database has been locked. Recruitment into the study will be terminated by the sponsor once the targeted number of randomized patients has been met or is foreseen to be met with the patients already in screening. Patients who have been screened and have a screening visit recorded in the IRT system at the time that the planned

enrollment number is met will be allowed to enter the trial and to be randomized if they are eligible.

Upon completion of their study participation, patients will return to individual treatment, as determined by their treating physician.

The investigator must provide follow-up medical care for all patients who are prematurely withdrawn from the study, or must refer them for appropriate ongoing care.

5.5.14 Early study termination

The study can be terminated by Novartis at any time for any reason. This may include reasons related to the benefit risk assessment of participating in the study, practical reasons, or for regulatory or medical reasons (including slow enrollment). Should this be necessary, the subject should be seen as soon as possible and treated as a prematurely withdrawn as described in [Section 5.5.9](#). The investigator may be informed of additional procedures to be followed in order to ensure that adequate consideration is given to the protection of the subject's interests. The investigator will be responsible for informing Institutional Review Board/Independent Ethics Committee (IRBs/ECs) of the early termination of the trial.

6 Visit schedule and assessments

[Table 6-1](#) lists all of the assessments, indicated with an "X" at the visits they are performed from screening to Week 52.

Patients should be seen for all visits on the designated day, or as closely as possible to the original planned visit schedule (recommended visit windows are in [Table 6-1](#)). Every effort should be made to respect the time frame for the Week 16 visit.

- For visits scheduled through Week 4, the study treatment should not be administered within less than 7 days after the previous administration
- For visits scheduled after Week 4, the study treatment should not be administered within less than 14 days after the previous administration

Patient Screening

Screening will be flexible in duration based on the time required to wash out prior anti-rheumatic medications and have a duration of up to 8 weeks before randomization. During which time the subject will sign the informed consent form (ICF), be evaluated for eligibility, and allowed sufficient time for medication washout, if required (see [Table 5-1](#)), in addition to other assessments indicated in [Table 6-1](#).

If patients do not have a chest X-ray available within 3 months of screening, the X-ray should be performed only after it is certain the subject meets inclusion/exclusion criteria in order to minimize unnecessary exposure to radiation.

Patients evaluated at visit 1 and 2 for Inclusion/Exclusion criteria should not be screen failed on the basis of a medication requiring washout, unless the subject will be unable to complete the washout in the appropriate time frame before randomization.

Premature Discontinuation

For patients who discontinue study treatment prematurely for any reason before the end of **Treatment Period 1**, (Visit 10/Week 16 EOT1) must be performed approximately four weeks after the last dose of study treatment (secukinumab 300 mg, secukinumab 150 mg or placebo). Patients should also be contacted via telephone, 84 days (12 weeks) after last dose of study drug, to inquire about any AE/SAEs that occurred during this period.

For patients who discontinue study treatment prematurely for any reason before the end of **Treatment Period 2**, (Visit 19/ Last visit EOT2) must be performed approximately four weeks after the last dose of study treatment (300 mg or 150 mg s.c. secukinumab). Patients should also be contacted via telephone, 84 days (12 weeks) after last dose of study drug, to inquire about any AE/SAEs that occurred during this period.

If patients refuse to return for these assessments or are unable to do so, every effort should be made to contact them or a knowledgeable informant by telephone to determine the reason.

At a minimum, patients will be contacted for safety evaluations during the 84 days (12 weeks) following the last study visit or following the last administration of study treatment (whichever is later), including a final contact at the 84-day point. Documentation of attempts to contact the subject should be recorded in the source documentation.

AE/SAE information obtained as a result of these calls must be recorded in the eCRF.

Unscheduled visits

Patients may be seen at any time for an unscheduled visit, e.g., if they experience deterioration or AEs that in the opinion of the investigator/qualified site staff need intervention or repeat laboratory testing. The assessment(s) performed at an unscheduled visit must include at minimum: an assessment of concomitant medication and procedures/significant non-drug therapies, vital signs, and an AE/SAE assessment. Any additional assessments performed are at the investigator/qualified site staff's discretion. During an unscheduled visit, study treatment will not be administered.

Table 6-1 Assessment schedule

Period	SCR ¹		Treatment Period 1								Treatment Period 2									Unscheduled Visit	
Week	-8 to BL		BL	1	2	3	4	8	12	16/EOT	20	24	28	32	36	40	44	48	52/EOT		Day 84 Safety Follow-up ⁴
Visit No	1	2	3	4	5	6	7	8	9	10	11	12	13	14	15	16	17	18	19		
Visit Window (days) ²				+/-2	+/-2	+/-2	+/-2	+/-2	+/-2	+/-2	+/-7	+/-7	+/-7	+/-7	+/-7	+/-7	+/-7	+/-7	+/-7		
Assessments																					
Obtain informed consent	X																				
Inclusion/exclusion criteria	X	X	X																		
Demographics	X																				
Psoriasis/PsA medical history / previous therapies	X																				
Relevant medical history/current medical conditions	X																				
Washout evaluation/instruction	X																				
PsA CASPAR criteria		X																			
Smoking and alcohol history			X																		
Cardiovascular medical history	X																				
Physical Exam ⁴		X	X	X	X	X	X	X	X	X	X	X	X	X	X	X	X	X	X		
Height		X																			

[figure not shown]

Weight		X	X							X									X			
Vital signs		X	X	X	X	X	X	X	X	X	X	X	X	X	X	X	X	X	X	X		X
Chest X-ray ⁵		X																				
ECG		X																				
Prior/Concomitant medication/ non-drug therapy	X	X	X	X	X	X	X	X	X	X	X	X	X	X	X	X	X	X	X	X		X
Randomization via IRT			X																			
Administration of sc study treatment via PFS at study site			X	X	X	X	X	X	X	X	X	X	X	X	X	X	X	X	X			
Adverse Events/SAEs ³ (incl. injection site reaction & occurrence of infections)	X	X	X	X	X	X	X	X	X	X	X	X	X	X	X	X	X	X	X	X	X	X
QuantIFERON TB-Gold test		X																				
Hematology, blood chemistry ⁶		X	X						X	X			X				X			X		
Serum pregnancy test		X																				
Urinalysis/Urine pregnancy test ⁷			X				X		X	X		X		X		X			X			
Anti-CCP	X																					
Rheumatoid factor (RF)	X																					
High sensitivity C-Reactive protein (hsCRP)		X	X	X			X	X	X	X	X	X	X	X	X	X	X	X	X	X		
Erythrocyte Sedimentation Rate (ESR) ⁷		X	X	X			X	X	X	X	X	X	X	X	X	X	X	X	X	X		
Tender and swollen joint		X	X	X			X	X	X	X	X	X	X	X	X	X	X	X	X	X		

Responder Status Assessment ⁹										X	X	X	X	X	X	X	X	X		
Treatment period 1 completion form										X										
Treatment period 2 completion form																		X		

¹ If washout period is ≤ 4 weeks, visit 1 & visit 2 can be performed the same day
² Patients who discontinued prematurely or withdrawn during a specific treatment period should return for a final visit. The final visit should be scheduled approximately four (4) weeks after the last study treatment, and should be performed before any new treatment is initiated
³ AEs/SAEs occurring after informed consent has been obtained must be reported. Patients who **discontinued prematurely** should be contacted **via telephone** to collect AE/SAEs information. Any AE/SAEs that occur in the following 84 days (12 weeks) after last dose of study drug must be reported.
⁴ These assessments are source documented only and will not be entered into the eCRF
⁵ Not necessary if done within past 3 months. If not, should be scheduled only after patient has met inclusion/exclusion criteria
⁶ Fasting sample
⁷ Tests performed locally using kits supplied by central lab
⁹ Those patients on secukinumab 150 mg who are non-responders at Week 16, 28, or 40 will start receiving secukinumab 300 mg s.c. every 4 weeks up to Week 48.

6.1 Information to be collected on screening failures

All patients who sign informed consent but discontinue prior to randomization at Visit 3 are considered screening failures. The IRT must be notified about the discontinuation, and the primary reason for the screen failure should be entered in the Screening Phase Disposition eCRF.

In addition, only the following eCRFs should be completed: Demography eCRF, Informed Consent eCRF, Inclusion/Exclusion eCRF, and the adverse event (AE) eCRF should be completed for any Serious Adverse Events (SAEs) that occurred during the screening period. Adverse events that are not serious will be followed by the investigator and collected only in the source data.

6.2 Patient demographics/other baseline characteristics

All baseline assessments should be performed prior to the first study treatment administration.

6.2.1 Demographics

Subject demographic and baseline characteristic data to be collected on all patients and recorded in the eCRF include:

- date of birth, subject initials, gender, race, and child-bearing potential (for females only).

6.2.2 PsA/Psoriasis history/ Prior psoriasis therapies

Disease history will be collected at the screening visit. The information to be collected and entered in the eCRF includes the following:

- date of first diagnosis of plaque psoriasis (by a physician)
- presence of psoriatic arthritis and the date of first diagnosis (by a physician)
- disease duration (if different from time since diagnosis)
- previous PsA/psoriasis treatments (including previous use of biologic therapies, as well as phototherapy and/or photo chemotherapy) and the reason for discontinuation of each therapy

6.2.3 Smoking history

The current and/or previous use of tobacco products will be recorded, as well as the estimated number of pack-years based on the approximate consumption per year. Non-smokers will be advised to not start smoking during the study.

6.2.4 Co-morbidities-Cardiovascular history

Any information pertaining to cardiovascular medical history assessed prior to signing informed consent should be reported on the Cardiovascular History eCRF.

6.2.5 Relevant medical history / Current medical conditions

Whenever possible, diagnoses and not symptoms will be recorded.

Relevant medical history/current medical conditions, not including psoriasis or psoriatic arthritis, will be recorded on the Medical History eCRF.

Relevant medical history/current medical conditions will include data up to six months prior to signing of the informed consent. Whenever possible, diagnoses (and not symptoms) will be recorded.

Significant findings that are observed after the subject has provided informed consent, and that meet the definition of an AE, must be recorded on the Adverse Event eCRF.

Investigators will have the discretion to record abnormal test findings on the Medical History eCRF when in their judgment, the test abnormality occurred prior to the informed consent signature.

6.2.6 Prior and concomitant medications

Concomitant medications and prior medications taken over the six months preceding study enrollment will be captured at the Screening visit, and updated at Visit 3 (Randomization).

6.2.7 Chest X-ray

A chest X-ray, CT scan, or MRI obtained within 3 months prior to randomization will be used to determine eligibility. If patients do not have a chest X-ray, CT scan, or MRI available within 3 months prior to randomization, a chest X-ray only must be done after it is fairly certain the subject meets the other inclusion/exclusion criteria in order to minimize unnecessary exposure to X-ray radiation for patients.

If the chest X-ray, CT scan, or MRI evaluated by a qualified physician shows evidence of ongoing infection or malignancy and the subject was not treated subsequent to the X-ray (CT scan or MRI), the subject will not be eligible to enter the study.

6.2.8 Determination of tuberculosis status

Determination of tuberculosis (TB) status will be required before administration of study treatment. TB status must be determined by medical history, signs, symptoms, and TB testing (QuantiFERON-TB Gold assay). Any significant findings will be recorded in the appropriate eCRF(s), as necessary.

If the QuantiFERON-TB Gold Assay test is positive or indeterminate, a TB workup should be performed as defined by local guidelines to determine the subject's TB status.

QuantiFERON TB-Gold In-Tube assay

A QuantiFERON[®] TB-Gold In-Tube assay will be performed to assess the TB status at screening for all patients. This test will only be used to determine subject's eligibility for the trial. The test will be used to screen the subject population for latent tuberculosis infection (Doherty et al 2008).

This blood-based assay is specific for Mycobacterium tuberculosis and is not influenced by previous Bacillus Calmette-Guérin vaccination or exposure to other Mycobacteria species.

This test, in contrast to the purified protein derivative (PPD) skin test, is also insensitive to a booster effect since the subject is not exposed to the vaccine. The assay measures the

production of interferon-gamma and presents it relative to a negative and a positive control sample ([Manuel and Kumar 2008](#))

The QuantiFERON®-TB Gold assay test will be supplied by the central laboratory. Details on the collection, shipment of samples and reporting of results by the central laboratory are provided in the Laboratory Manual.

The results of a TB workup for a subject with a positive or indeterminate test must be recorded in the eCRF.

- If the test result is **negative**, the subject may be randomized.
- If the test result is **positive**, the investigator should perform a TB workup for the test result as per local procedures.
- Patients **positive** for latent TB per workup may be randomized to the trial if sufficient treatment has been initiated according to local routine clinical practice and will be maintained for the prescribed duration.
- Patients **positive** for active TB per workup are not eligible for the study.
- Patients **negative** for TB (no signs of latent or active TB) per workup may be randomized to the trial.
- If the test result is **indeterminate**, it is **recommended to repeat the test once**. The investigator may decide to skip the repetition of the test and proceed directly to the workup (however this is not recommended). If a TB workup was conducted prior to screening, results from the workup can be used to assess eligibility if the workup was conducted within 12 weeks prior to randomization.
- If the second test is negative, the subject may be randomized.
- If the second test is positive or indeterminate, the investigator should perform a TB workup as per local guidelines. The subject will not be eligible for randomization if: “active tuberculosis is present”, or if “latent tuberculosis is present” and is untreated as per local guidelines.

6.3 Treatment exposure and compliance

All doses of secukinumab or placebo administration will be recorded on the Dosage Administration Record eCRF. Compliance will be assessed by Novartis and CRO study personnel using the Dosage Administration Record eCRF, medication numbers, Drug Label Form information, and information collected by IRT.

Compliance is expected to be 100% since all doses of study treatment will be administered **at the site** in the presence of the investigator or site staff, unless temporary interruption is needed for safety reasons as described in [Section 5.5.5](#).

[figure not shown]
6.4 Efficacy

The primary efficacy variable is ACR20 response (yes, no). The primary analysis time point will be at Week 16.

The secondary efficacy variables are the following:

1. Dactylitis (yes, no)
2. Enthesitis (yes, no)
3. ACR50 response (yes, no)
4. ACR70 response (yes, no)
5. Minimal Disease Activity (yes, no)
6. PASI75 response (yes, no)
7. PASI90 response (yes, no)
8. PASI100 response (yes, no)
9. Change from baseline in DAS28-CRP
10. Change from baseline in PASDAS
11. Change from baseline in SF12
12. Change from baseline in HAQ-DI

6.4.1 American College of Rheumatology (ACR) response

The ACR response ([Appendix 4](#)) will be used to determine efficacy ([Felson 1995](#))-*A subject is defined as e.g. an ACR20 responder if, and only if, the following three conditions hold:

- they have a $\geq 20\%$ improvement in the number of tender joints (based on 78 joints)
- they have a $\geq 20\%$ improvement in the number of swollen joints (based on 76 joints)
- they have a $\geq 20\%$ improvement in three of the following five domains:
 - Patient's global assessment of disease activity (measured on a VAS scale, 0-100)
 - Physician's global assessment of disease activity (measured on a VAS scale, 0-100)
 - Patient's assessment of PsA pain (measured on a VAS scale, 0-100)
 - Health Assessment Questionnaire (HAQ[®]) score
 - Acute phase reactant (hsCRP or ESR)

ACR50 = 50 % improvement in at least 3 of the 5 domains and 50 % improvement in the swollen and tender joint count.

ACR70 = 70 % improvement in at least 3 of the 5 domains and 70 % improvement in the swollen and tender joint count.

The ACR response is to be assessed at the visits/time points shown in [Table 6-1](#).

6.4.2 Tender 78 joint count and swollen 76 joint count

Joint counts will be performed by the assessor(s) who must be well trained and part of the site personnel. Whenever possible, the same evaluator should perform these assessments at all visits.

The 78 joints assessed for tenderness include the 2 temporomandibular, 2 sternoclavicular, 2 acromioclavicular joints, 2 shoulders, 2 elbows, 2 wrists, 2 first carpometacarpal, 10 metacarpophalangeal, 10 proximal interphalangeal, 8 distal interphalangeal joints of the hands, the 2 hip, 2 knee, 2 talo-tibial, 2 mid-tarsal, 10 metatarsophalangeal, 10 proximal interphalangeal, and 8 distal interphalangeal joints of the feet. All of these except for the hips are assessed for swelling. Joint tenderness and swelling are to be graded present (1) or absent (0). Synovial fluid and/or soft tissue swelling but not bony overgrowth represents a positive result for swollen joint count. Dactylitis of a digit in the foot or hand counts as one tender and swollen joint.

Data is recorded for tender and swollen joints (right or left side), i.e. a box (no, yes or not applicable) needs to be ticked for all joints. The total number of tender and swollen joints (right and left) will be automatically calculated in the eCRF.

6.4.3 Patient Reported Outcomes (PRO)/QoL Assessments

[figure not shown]
Patients should complete all assessments prior to any investigator evaluations.

- Patient's Assessment of PsA pain intensity
- Patient's global assessment of disease activity (VAS)
- Patient's global assessment of psoriasis and arthritis disease activity (VAS)

The impact of PsA on various aspects of patients' health-related quality of life (HRQoL) will be assessed using the following validated instruments:

- Health Assessment Questionnaire (HAQ-DI)
- SF-12

All questionnaires will be completed at the defined visits/ time points listed in [Table 6-1](#), and prior to the subject seeing the investigator for any clinical assessment or evaluation. The subject should be given sufficient instruction, space, time and privacy to complete the questionnaires. The study coordinator should check the questionnaires for completeness and encourage the subject to complete any missing responses. Completed questionnaires should be reviewed and assessed by the investigator before the clinical examination, for responses which may indicate potential AEs or SAEs. This assessment should be documented in the source records. If AEs or SAEs are confirmed the investigator should record the events as per instructions given in the relevant section of the protocol (see [Section 7](#)).

Guidelines for administering the PRO questionnaires can be found in [Appendix 10](#).

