6.4.4 Physician's global assessment of disease activity

The physician's global assessment of disease activity will be performed using 100 mm VAS ranging from no disease activity to maximal disease activity, after the question "*Considering all the ways the disease affects your patient, draw a line on the scale for how well his or her condition is today*". To enhance objectivity, the physician must not be aware of the specific patient's global assessment of disease activity, when performing his own assessment on that subject.

[figure not shown]

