The HAQ[®] is to be completed by the patients in their local languages, using an electronic device. The questionnaires should be completed by the patients in a quiet area free from disturbance, and before any visit assessments. Patients should receive no help from family members; if questions cannot be answered alone (due to problems with reading or understanding), then the doctor or nurse should read the questions and record the patient's responses without influencing their answers. The information provided is strictly confidential and will be treated as such. If a patient has missed a question or given more than one response per question, then this should be brought to patient. Incomplete questions should not be accepted without first encouraging the patient to complete unanswered questions.

The investigator must complete the patient/visit information on the electronic device and ensure that the center number, patient's number and initials are identical to the Case Record Form. As there are no source data for this questionnaire, the data queries will be restricted to patient/visit information.

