In these instances, the coordinator may obtain patient responses by reading out loud each question, followed by the corresponding response categories, and entering the patient's response. No help should be provided to the patient by any person other than the designated study coordinator. The coordinator should not influence patient responses. The study coordinator cannot translate the question into simpler language and has to be read verbatim.

The patient wants someone else to complete the questionnaire(s)

In no case should the coordinator or anyone other than the patient provide responses to the questions. Unless specified in the study protocol proxy data are *not* an acceptable substitute for patient self-reported. Patients should be discouraged from asking a family member or friend for help in completing a questionnaire.

The patient does not want to finish completing the questionnaire(s)

If non-completion is a result of the patient having trouble understanding particular items, ask the patient to explain the difficulty. Re-read the question for them *verbatim*, but do not rephrase the question. If the respondent is still unable to complete the questionnaire, that questionnaire will be forfeited since partial response will not be saved. Thank the patient.

The patient is concerned that someone will look at his/her responses

Emphasize that all responses are to be kept confidential. Point out that their names do not appear anywhere on the questionnaire, so that their results will be linked with an ID number and not their name. Tell the patient that his/her answers will be pooled with other patients' answers and that they will be analyzed as a group rather than as individuals. Tell the patient that completed questionnaires are not routinely shared with treating staff, and that their responses will only be seen by you and possibly the investigator. Any response which may directly impact on or reflect their medical condition (e.g. noting of severe depression) will be communicated by the coordinator to the physician.

The patient asks the meaning of a question/item

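### Protocol 6.4.3 has the investigator review the patient's global score before the examination, while 6.4.4 bars the physician from knowing it; where one person does both, the physician's global is no longer rated independently.

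*Protocol*

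**What the plan says.** Protocol Section 6.4.3 lists three patient VAS items (pain, global disease activity, and global psoriasis and arthritis activity) together with HAQ-DI and SF-12. All are completed "prior to the subject seeing the investigator for any clinical assessment or evaluation". The section continues: "Completed questionnaires should be reviewed and assessed by the investigator before the clinical examination". The stated aim is to find answers that could signal an AE or SAE.

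Protocol Section 6.4.4 is a prohibition. It begins "To enhance objectivity, the physician must not be aware of the specific", and the score it names is the patient's global for the person being assessed, at the time the physician marks the physician's global VAS.

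Three other places bear on who sees the answers:

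- The Amendment 1 rationale, explaining why the independent joint assessor was dropped, leaves it to the investigator to decide who performs the evaluations.
- Appendix 8 (HAQ) says that if a patient cannot manage the questions alone, "then the doctor or nurse should read the questions" and record the responses. The general information in Appendix 10 extends reading aloud by the doctor or nurse to all questionnaires. Elsewhere in Appendix 10, a patient who is too ill or weak may be helped only by the designated study coordinator.
- Appendix 10 has patients told that "completed questionnaires are not routinely shared with treating staff" and that the coordinator, and possibly the investigator, will see them.

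**The concern.** Section 6.4.3 sets an order: patient completes the questionnaires, investigator reviews them, investigator examines the patient. An investigator who follows that order and then marks the physician's global VAS has already had access to the one score that 6.4.4 says must be unknown at that moment.

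The protocol itself gives objectivity as the reason for the masking. The physician's global is one of the five domains behind the ACR20, ACR50 and ACR70 responses, and it is a term in PASDAS. The SAP's revision table also lists a physician's global response among the Week 52 analyses. If the physician's mark is anchored on the patient's mark, the three-of-five rule partly counts one patient report twice.

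**Working it through.** **Can both instructions be followed?**

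| Question | Section 6.4.3 | Section 6.4.4 |
|---|---|---|
| Who acts? | The investigator | The physician |
| When? | Before the clinical examination | When scoring the physician's global |
| Patient's global VAS | Among the listed measures; not exempted | Must not be known |
| Force | Should | Must not |

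No section exempts the VAS from the review, places the review after the physician's score, or requires a different rater. Both instructions can be followed if a second person scores the physician's global, or if the review is taken to cover only HAQ-DI and SF-12. The protocol states neither. If one person reviews everything listed and then scores, 6.4.4 is not met.

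**Size: inputs.** The plan gives no figure on this point, and none of its stated figures changes. The assumed ACR20 rates of 50% on 300 mg and 20% on placebo (Protocol 9.7; SAP 3) are used below only for calibration. The documents give no component improvement rates, correlations or anchoring strength, so those are assumptions.

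**Check A: three-of-five rule, loss of independent rating only.** Take five latent normal scores with a common correlation r. Component i is improved if Z_i < Φ⁻¹(p), and the rule is met if at least three are improved. Raise only the correlation between the two globals, from r to 0.95. The change in P(at least 3 of 5), in percentage points from unrounded values, is:

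| p for each component | r = 0.3 | r = 0.5 | r = 0.7 |
|---|---|---|---|
| 0.3 | +1.6 | +0.9 | +0.4 |
| 0.4 | +0.9 | +0.5 | +0.1 |
| 0.5 | -0.1 | 0.0 | 0.0 |
| 0.6 | -0.9 | -0.5 | -0.2 |
| 0.7 | -1.6 | -0.9 | -0.4 |

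For example, at p = 0.3 and r = 0.3 the probability goes from 0.228 to 0.244. The joint-count conditions are left out, and no shift in the physician's mean score is modelled.

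**Check B: full ACR20 rule with anchoring.** Take seven improvement scores with common correlation 0.4 or 0.6, and set the means so that ACR20 is 20% or 50%. Simulate 400,000 patients per arm. Replace the physician's score by

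PhGA* = (1 - w) × PhGA + w × PtGA, with w = 0.3, 0.5 or 0.7.

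- Patients whose ACR20 status changes: about 0.4% to 2.6%. At the upper end that is 0.026 × 100 = 2.6 patients in an arm of 100 and 0.026 × 50 = 1.3 in an arm of 50.
- Net change in the ACR20 rate per arm: between about +0.1 and -0.7 points. The difference between two arms can therefore move by at most 0.1 + 0.7 = 0.8 points, against the 50 - 20 = 30 points assumed.
- Patients whose 20% improvement status on the physician's global itself changes: about 8% to 26%.

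**PASDAS weights.** With the final factor of 1.5 applied to the whole sum (Protocol 6.4.9), the physician's global enters as 1.5 × 0.18 = 0.27 per unit of √VAS, and the patient's global as 1.5 × 0.159 = 0.2385. The effect of anchoring on PASDAS was not simulated.

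**The case against.** The strongest reply is that a careful site can satisfy both sections. The 6.4.3 review is a safety screen, limited to answers that may point to adverse events. Appendix 10's example of a worrying answer is an SF-12 item, and 6.4.3 introduces HAQ-DI and SF-12 as the instruments just before it speaks of questionnaires. Section 6.4.4 is specific and mandatory, 6.4.3 general and advisory. The investigator may also give the physician's global to someone else.

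All of that is available, but none of it is written. Protocol 8.3 treats the patient-reported measures generally as questionnaires completed on the tablet, and sites may resolve the conflict differently. The reply therefore limits how often the safeguard fails; it does not remove the conflict.

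The reply does rule out several stronger readings that a reader might infer:

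- That 6.4.4 is broken at every site and visit. This holds only where one person does both tasks.
- That two ACR components lose statistical independence. They measure the same disease and never had it; what is lost is independent rating.
- That pain, HAQ-DI or the joint counts should also be masked. Section 6.4.4 protects only the patient's global.
- That Appendix 10 bars the investigator from the answers. It says the investigator may see them; the fault is only that 6.4.3 makes the review standard.
- That PASDAS counts one patient score twice. Section 6.4.9 describes a separate patient global, covering psoriasis and arthritis over the past week, whereas 6.4.4 names the patient's global of disease activity.

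**Conclusion.** The point stands as an internal inconsistency between Protocol 6.4.3 and 6.4.4. It defeats a stated safeguard wherever the person who reviews the questionnaires also scores the physician's global.

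For ACR20 the effect is small: roughly 0.4% to 2.6% of patients reclassified and less than 1 point net per arm. It falls more directly on the physician's global as a measure in its own right. These sizes rest on equal correlations of 0.4 or 0.6 and anchoring weights of 0.3 to 0.7, none of which comes from the documents.

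A reader might infer that the primary comparison is biased towards the drug. The documents do not support that: Protocol 5.4 keeps investigators and assessors blinded to individual treatment assignment, and no mechanism favouring one arm is shown. The case for changing the text is that the protocol should deliver its own safeguard, at almost no cost.

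**What to change.** Add one sentence to Protocol 6.4.3, for example: *The patient's global VAS scores are excluded from the investigator's pre-examination AE review and are not shown to the person scoring the physician's global until that score is recorded; the review of the other questionnaires for AEs/SAEs is unchanged.* The plural covers both global VAS items. Section 6.4.4 strictly requires only the disease-activity one, and including the second avoids the same question for PASDAS.

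Align the read-aloud wording in Appendices 8 and 10 with the designated-coordinator rule already in Appendix 10. For the 6.4.4 safeguard the Appendix 10 wording matters most, because it covers all questionnaires and so includes the patient's global. Appendix 8 concerns only the HAQ and is changed for consistency.

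Reword the confidentiality statement in Appendix 10 so that patients are told of the investigator review that 6.4.3 makes routine.

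The cost is protocol wording and a memo to sites. The rater sees the patient's global VAS slightly later in the same visit. Adverse-event screening is not moved to anyone else, and no extra staff are needed.
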